Alzheimer's disease and related dementia are dreaded conditions and people are seeking answers. Even though no cure is in sight, patients and families seek help in managing behavioral symptoms and health care decision-making.²¹⁻²⁴ It is of little wonder that primary care physicians find themselves in a situation of therapeutic nihilism, cynicism, low levels of confidence, and frustration.²⁵⁻²⁷ Our prior explanatory trial demonstrated that primary care providers, given the proper resources, can improve behavioral and psychological symptoms associated with dementia, caregiver stress, and depression.

The objective of this proposal is to address the question of whether the benefits outweigh the harms of routine screening for dementia among older adults in primary care when the screening program is coupled with primary care practices prepared to provide care for those who screen positive. All subjects will complete a screening questionnaire that includes screening already recommended for older adults (e.g. smoking). A random sample of these subjects will have a cognitive screener embedded within this larger set of screening questions. Thus, the control condition (no screening) means no cognitive screener.

The proposed project will contribute important information to patient, families, providers, and policy-makers about the harms and benefits of routine screening for dementia. If this trial is successful, it will not only address the appropriateness of routine screening for dementia, it will also provide a template for the successful implementation of screening programs, coupled with diagnosis and treatment programs, that are practical for a broad range of health care systems. Finally, we will report data on cost and cost effectiveness.

The specific aim of the study is to conduct a pragmatic randomized clinical trial assessing the harms and benefits of screening for dementia, compared to no screening for dementia, among 4,000 typical, older adults, cared for in typical, primary care practices, prepared to deliver best practices dementia care.

Primary Specific Aim 1: Test the impact of dementia screening on health-related quality of life of the patient at baseline and at 1, 6, and 12 months.

(We hypothesis that screened subjects, compared with non-screened subjects, will have a higher health-related quality of life as measured by the Health Utility Index (HUI) at 12 months post-screening.)

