Primary Specific Aim 2: Test the impact of dementia screening on the mood and anxiety symptoms of patient at baseline and 1, 6, and 12 months (i.e., primary potential harms).

(We hypothesize that screened subjects will not have higher depression or anxiety at one month post-screening (as measured by the Patient Health Questionnaire (PHQ-9) and Generalized Anxiety Disorder (GAD-7) scales)

Secondary Aims: Estimate the cost effectiveness of dementia screening.

(We hypothesize that screened subjects will have an Incremental Cost Effectiveness Ratio (ICER) below the maximum acceptable threshold of \$100,000 per quality adjusted life year saved at 12 months.)

B. Innovation

Pragmatic

Previous studies by our team and others have demonstrated that routine feedback of dementia screening scores, continuing medical education for dementia, and other passive educational interventions can improve rates of diagnosis, but not patient outcomes.^{12,28-32} We have shown that patients and families perceive potential harms from screening and that dementia screening can result in important incremental health care costs.^{21-23,33} Conversely, we and others have also already demonstrated that collaborative care, focused on non-

pharmacologic approaches to behavioral disturbances, can improve patient outcomes under experimental conditions.^{34,35} The innovation of this trial is in moving the process upstream to asymptomatic, older adults, cared for in typical but prepared community-based practices, to document actual benefits and harms, including costs. “Asymptomatic”, in the case of cognitive impairment, is paradoxical in some respects, but we denote asymptomatic to mean that the cognitive impairment is not a presenting symptom of the patient (just as hypertension is asymptomatic but can be detected by screening, cognitive impairment can be detected through screening tests).

Academic Community Partnership

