determine the subject's HRQOL.¹¹¹ The HUI is a generic, utility-based HRQOL instrument applied in patients with a wide range of medical conditions.^{111,112} It has eight attributes: Vision, hearing, speech, ambulation, dexterity, emotion, cognition and pain. The individual health domain scores range from 0.00 (maximum impairment) to 1.00 (no impairment) and the multi-attribute (HUI index) scores, a multiplicative function of individual attribute levels, range from 0.36 to 1.00 with anchors 0.00 = dead and 1.00 = perfect health. Naglie et al found that test-retest reliability exceeded the standard for adequate reliability of 0.70 in those with mild dementia (ICC = 0.75).¹¹³ [name] recently published a paper that provides new evidence regarding the construct validity (including responsiveness) of the HUI in community-based subjects with dementia.¹¹² The mean HUI multi-attribute utility score for 408 primary care patients with dementia was 0.54 (SD = 0.23) and the mean one year change was -0.30 among 240 dementia patients who remained in their own home after one year of receiving dementia care program whereas the mean one year change was -0.76 among 29 dementia patients who moved into a skilled nursing home facility.¹¹²

Mood and Anxiety Outcomes

We will use the **Patient Health Questionnaire–9 (PHQ-9)**¹¹⁴⁻¹¹⁶ and **Generalized Anxiety Disorder Scale (GAD-7)**^{117,118} to determine the impact of screening on our subjects' mood and anxiety at baseline, 1,6, and 12 months. We have used both instruments in various primary care-based research studies including our dementia collaborative care trial.^{34,51,93,114-118} The PHQ-9 is a nine-item depression scale with a total score from 0 to 27 and the GAD-7 is a seven-item anxiety scale with a total score from 0 to 21. Both of these scales are derived from the Patient Health Questionnaire; have good internal consistency and test–retest reliability; as well as convergent, construct, criterion, procedural and factorial validity for the diagnosis of major depression and general anxiety disorder.¹¹⁴⁻¹¹⁸ In our previous primary care studies, the mean

PHQ-9 scores ranged from 3.8 (SD = 5.1) to 4.4 (SD = 5.6) and the mean GAD scores ranged from 2.7 (SD = 3.2) to 3.2 (SD= 3.5).^{34,114-118}

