The outcome measures for this study are HRQOL (HUI multi-attribute utility score), mood (PHQ-9) and anxiety levels (GAD-7) obtained at baseline, 1, 6, and 12 months. To verify the comparability of the randomized groups, patients' baseline characteristics between the screened and no screening groups will be compared using *t*-tests for continuous variables and chi-square tests for categorical variables. We will carefully examine the distributions of continuous variable and use alternative approaches such as transformation or nonparametric methods in cases of violation to the normal distribution assumption. We will also examine the frequency distribution of all categorical variables and adopt exact inference procedures in cases of zero or small cell size. We will compare the baseline characteristics between subjects with missing outcomes due to death or refusal at 12 months to subjects who completed the follow-up

to detect potential violation to the missing at random assumption. Further sensitivity analyses will be performed using various methods of imputation or a full parametric likelihood approach assuming various patterns of missing data.¹²²

Primary Aim tests the hypothesis that subjects in the dementia screening group will have higher health-related quality of life compared those in the no screening group. We will compare mean measures of health-related quality of life levels in the “screening” group to the “no screening” group using analysis of covariance (ANCOVA) while including baseline measures as covariates. We will first conduct the ANCOVA models separately for outcomes obtained at 12 months while adjusting for baseline measures. We will then use the mixed effect models to examine whether the difference between the two groups changes over time using repeated HUI measures as the dependent variables, group, time, interaction between group and time as independent variables while controlling for other baseline covariates. All analyses will be conducted using SAS 9.3 (SAS Institute, Carey, North Carolina). For the patients who do not complete the 12 month surveys for health-related quality of life, they will be excluded from the analyses followed by sensitivity analyses on missing data described below.

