Secondary Aim 1 compares depression and anxiety levels at 1 month post dementia screening between screened subjects and subjects in the no screening group. ANCOVA models will be used to compare PHQ-9 and GAD-7 obtained at 1 month between the screening and no screening groups adjusting for patients’ characteristics and baseline measures.

Secondary Aim 2 estimates the cost effectiveness of the dementia screening program in comparison to the “no screening”. This economic evaluation will be conducted from the societal and payer perspectives, including the direct medical care costs, caregiver and patient time and transportation costs, and the effect on quality of life for patients and caregivers.¹²³ Costs will be

divided into fixed and variable costs and by the screening, initial assessment phase and the follow-up phase of treatment. Total medical care utilization costs will be estimated for the control and screening groups from healthcare utilization and reimbursement data captured by the Indiana Network for Patient Care (INPC) during the trial. Prescription drug use will also be obtained from the INPC healthcare administrative database. The cost analysis will capture the extent to which screening, early diagnosis and coordinated care of patients with Alzheimer's disease affects medical care costs associated with dementia and co-morbid conditions such as diabetes, made worse by failure to manage dementia. Activity costing will be utilized to estimate the costs necessary to implement and operate the screening and collaborative dementia care management program and the usual care for dementia patients. Patient and caregiver time, staff time, fringe benefits, overhead costs, and materials will be logged by staff using the eMR-ABC software and assessed for the 12 month follow-up period. Included are waiting time, time with patients, time in meetings, lab services, telephone calls and mailings to participants. Excluded are costs associated with research. Transportation costs will be estimated from data on distance from home to clinic. Health care contacts will be dated and checked to avoid double counting via claims and activity costing methods.

Prescription drugs will be valued at the median wholesale price. A dispensing fee will be added for each 100 doses. Unit wage costs and fringe benefits will be standardized applying median values paid to personnel in the region; wage data collected from the health care system partners.

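### Aim 2 covers mood and anxiety at 1, 6 and 12 months, but the plan specifies no between-arm PHQ-9 or GAD-7 analysis after month 1

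*Combined protocol and SAP*

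**What the plan says.** The aims at the start of the combined protocol and SAP set Primary Specific Aim 2 as: "Test the impact of dementia screening on the mood and anxiety symptoms of patient at baseline and 1, 6, and 12 months". They describe these symptoms as the main potential harms. The hypothesis under the aim is narrower: "screened subjects will not have higher depression or anxiety at one month post-screening".

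Section H (Data Collection, Mood and Anxiety Outcomes) schedules both scales at every visit. Section I (Statistical Plan) opens by listing the trial's outcome measures, among them "mood (PHQ-9) and anxiety levels (GAD-7) obtained at baseline, 1, 6, and 12 months".

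Section I then gives the analyses:

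- **Primary Aim paragraph (health-related quality of life).** An ANCOVA at 12 months, followed by a mixed model with group, time and their interaction, "using repeated HUI measures as the dependent variables".
- **Secondary Aim 1 paragraph (the label Section I gives to Aim 2).** "ANCOVA models will be used to compare PHQ-9 and GAD-7 obtained at 1 month", adjusted for patient characteristics and baseline scores.

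The power statement for the two scales in Section I and the mood and anxiety reporting milestone in Section K (Time Line) also refer to one month only.

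**The concern.** The trial's stated objective is to establish "whether the benefits outweigh the harms of routine screening for dementia among older adults in primary care". The benefit hypothesis is "higher health-related quality of life as measured by the Health Utility Index (HUI) at 12 months post-screening". Followed as written, the plan tests benefit at month 12 and compares the named harm scales only at month 1, although the same interviews collect those scales at months 6 and 12.

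The plan does not claim absence of mood or anxiety harm through 12 months, so no false statement is built in. What is at stake is the weighing of benefit against harm. At the visit where benefit is judged, any PHQ-9 or GAD-7 result would be unplanned and, favourable or not, open to a charge of selective reporting.

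Timing may add to this. Section E (The Collaborative Dementia Care Program) has the diagnosis explained at a second home visit, planned two to four weeks after the first. No section states the wait from screening to the first home visit. For some participants the 1-month interview may come before, or only just after, they learn of a diagnosis. That is a possibility, not a documented timetable, and the point does not depend on it.

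**Working it through.** **1. Aim against analysis, visit by visit**

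| Visit | In Aim 2 | PHQ-9/GAD-7 collected | Between-arm PHQ-9/GAD-7 analysis specified |
|---|---|---|---|
| 1 month | yes | yes | yes (ANCOVA) |
| 6 months | yes | yes | none |
| 12 months | yes | yes | none |

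**2. Inputs**

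- From Section I: 4,000 participants; margin 0.6 with SD 5.1 for PHQ-9; margin 0.5 with SD 3.2 for GAD-7; 10% missing outcomes at 12 months.
- From Section E: 1:1 allocation, so 2,000 per arm, or 1,800 after 10% loss; 300 expected screen-positives and 100 expected diagnoses in the screened arm.
- Assumed, because the plan does not state them: equivalence tested by two one-sided tests (TOST) at 0.05 per side; a true difference of 0; the 1-month margins and SDs carried to later visits.

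**3. The plan's own figure (power above 95% at 1 month)**

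SE = SD × √(2/n); TOST power = 2Φ(margin/SE − 1.645) − 1. With n = 2,000 per arm:

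- PHQ-9: SE = 5.1 × √(2/2000) = 0.161; power = 96.2%.
- GAD-7: SE = 3.2 × √(2/2000) = 0.101; power = 99.9%.

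The stated figure reproduces.

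**4. What a 6- or 12-month contrast would deliver (n = 1,800 per arm, no baseline adjustment)**

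- PHQ-9: SE = 5.1 × √(2/1800) = 0.170; 95% CI half-width = 1.96 × 0.170 = 0.333; TOST power = 94.1%; one-sided 0.05 power = Φ(0.6/0.170 − 1.645) = 97.0%.
- GAD-7: SE = 3.2 × √(2/1800) = 0.107; half-width = 0.209; TOST power = 99.8%; one-sided power = 99.9%.

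Both half-widths lie well inside the plan's 1-month margins.

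**5. If a no-harm claim had to hold at all three visits together**

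Simulated with 2,000,000 draws, assuming equal between-visit correlations of 0.3, 0.5 and 0.7, again without baseline adjustment:

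| PHQ-9 | TOST power | One-sided 0.05 power |
|---|---|---|
| 10% loss at every visit | 84.0 / 85.3 / 87.2% | 92.0 / 92.7 / 93.6% |
| No loss at month 1, 10% at months 6 and 12 | 85.8 / 86.9 / 88.5% | 92.9 / 93.5 / 94.3% |

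GAD-7 exceeds 99% throughout.

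**6. Dilution**

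Mean worsening that a subgroup would need for the arm mean to move by the margin:

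- Diagnosed: 100/2,000 = 5%; 0.6/0.05 = 12 PHQ-9 points; 0.5/0.05 = 10 GAD-7 points.
- Screen-positive: 300/2,000 = 15%; 0.6/0.15 = 4.0 PHQ-9 points; 0.5/0.15 = 3.3 GAD-7 points.

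**The case against.** The strongest reply is that the visits in Aim 2 are an assessment schedule. The list includes baseline, where no effect of screening can be tested, and the hypothesis beneath it fixes the test at one month. The ANCOVA, power statement and milestone all agree with that hypothesis. This stands as far as it goes: the confirmatory test is coherent. It does not close the gap. Aim 1 is worded in the same form, yet for HUI the plan adds a model across visits; for PHQ-9 and GAD-7 it adds nothing.

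A generous reader might take the 12-month ANCOVA, which refers to outcomes in the plural, to include the harm scales. That sentence sits in the quality-of-life paragraph, the mixed model that follows names HUI alone, and depression and anxiety are then treated separately at month 1. If the wider meaning was intended, a sentence saying so is still needed.

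Partial cover elsewhere does not replace the comparison. HUI includes emotion, but as one of eight attributes: "Vision, hearing, speech, ambulation, dexterity, emotion, cognition and pain". The monitoring board in Section M reviews anxiety and depression as safety monitoring, with no comparison method given.

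Two limits on the remedy stand. A whole-arm contrast mainly reflects the roughly 85% expected to screen negative, so it says little about harm confined to those diagnosed. The three-visit power figures apply only if a claim needs all three visits, and they ignore baseline adjustment. With an assumed baseline correlation of 0.5, single-visit PHQ-9 TOST power at 1,800 per arm rises from 94.1% to about 98.5%.

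**Conclusion.** The concern holds. The plan specifies no between-arm PHQ-9 or GAD-7 analysis at 6 or 12 months, so Aim 2 goes unanalysed at two of its three follow-up visits, one of them the visit at which benefit is tested. This conclusion comes from reading the text and needs no numerical assumption.

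The calculations show only that the missing contrasts would be worth having for the average effect of being screened (about ±0.33 PHQ-9 and ±0.21 GAD-7 points), given the plan's SDs and 10% loss. The power figures also rest on the assumed test level, carried-over margins and correlations.

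The 1-month harm test and the 12-month HUI test are unaffected. This should be corrected, but it does not invalidate the trial.

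**What to change.** Amend Section I as follows:

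- Keep the 1-month ANCOVA as the confirmatory harm test.
- Fit the mixed model already described for HUI (group, time, group-by-time) to PHQ-9 and GAD-7, adjusting for the baseline score.
- Report the screening-minus-control contrast with its confidence interval at 1, 6 and 12 months, and label the 6- and 12-month contrasts secondary.
- Limit any statement of no harm to the visits whose contrasts support it. The 0.6 and 0.5 margins are given for one month only; if they are used later, record that as an explicit choice.
- State that the whole-arm contrast is diluted for the roughly 5% expected to be diagnosed and cannot rule out harm confined to them.

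If the later analyses are not intended, narrow Aim 2 to one month instead.

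The cost is SAP wording and a little more analysis. No new visits, data or participants are needed, and the 1-month claim is unaffected. Only a claim that requires all three visits together would have lower PHQ-9 power, as tabulated above. The change does not cure dilution.

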The director of the clinical core ([name]) will meet with the Advanced Practice Nurse on a weekly basis to review the performance of the program, its fidelity and any complicated care using the electronic reports generated by the care coordination support software (eMR-ABC). The eMR-ABC will provide [name] with a weekly report of the performance of the care coordinator in regards to the adherence of delivering specific protocols.

The Usual Care Control Groups:

The 2,000 subjects who would be randomized into the “no screening group” will continue to receive their usual care, including a referral to the local memory care practices if their primary care provider suspects the presence of a cognitive problem at any time during the study follow-up.

Overview of Data Sources		
Construct	Source of data	Specific variables/Instruments
Social, Demographic, Advance care planning	Study Survey	MOS, age, gender, race, education, income, living situation, marital status, and advance care planning
Health Related Quality of Life, Mood and Anxiety	Study Survey	HUI, PHQ-9, GAD-7
Health Care Utilization	Indiana Network for Patient Care records for the 4000 subjects	ER episode, location
		Hospital episode, location
		Inpatient diagnoses (ICD9 codes)
		Length of stay
Co-morbidity	Indiana Network for Patient Care records for the 4000 subjects	ICD-9 codes for the 10 common chronic diseases

Medication Use	Indiana Network for Patient Care records for the 4000 subjects	Psychotropics
Care Processes	eMR-ABC and INPC	Visits to memory care practice. Collaborative dementia care team visit. Visits with HABC monitor Protocols delivered by the care team

F. Inclusion/Exclusion Criteria

Inclusion criteria include:

- adults age 65 and older;
- at least one office visit to their primary care physician within the previous year;
- no previous diagnosis of dementia or memory problem as determined by ICD-9 codes or the presence of prescription for anti-dementia medications (cholinesterase inhibitors or memantine);
- ability to consent to participate in the study; and
- ability to communicate in English

[figure not shown]
Exclusion criteria include:

- adults who are a permanent resident of a nursing facility;
- a serious mental illness such as bipolar disorder or schizophrenia as determined by the presence of related ICD-9 codes indicative of such an illness; or
- a pre-existing diagnosis of dementia or cognitive impairment

G. Enrollment/Randomization

Clinical Settings and Population

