Costs will be accumulated during the trial based on the probability of survival each month times the monthly cost of care for survivors to address censoring.¹²⁴ Effects and costs will be discounted at a 3% annual rate for the two-year trial period. The incremental CE ratio (ICER), will compare the no screening and less resource intensive usual care treatment strategy (UC) with the screening coupled with the more intensive treatment intervention (the

collaborative dementia care program) using the following formulas for (1) dementia patients (AP) and (2) Dementia patients plus their caregivers (CG).

$$ICER_{AP} = [COST_{HABC} - COST_{UC}] \div [QALY_{HABC} - QALY_{UC}] \quad (1)$$

$$ICER_{AP+CG} = [COST_{HABC} - COST_{UC}] \div [QALY_{HABC} - QALY_{UC}] \quad (2)$$

Uncertainty in the cost-effectiveness ratios and 95 percent confidence intervals will be assessed with 1,000 bootstrap samples. The outcome of each sample will be expressed as a scatter plot of incremental costs and effects generated from the bootstrap samples, reflecting the uncertainty arising from the model parameters. Results will also be displayed using net benefit analysis and cost-effectiveness acceptability curves (CEAC).¹²⁵ There is controversy about the appropriate ceiling ratio for health benefits.¹²⁶ Garber et al have recommended that a value of twice the median annual per capita income will result in efficient resource allocation.¹²⁶ The effects on ICERs of alternative unit cost estimates for care-giver time value and overhead cost rate for the screening and coordinated care management will be examined in a series of one-way and multi-way sensitivity analyses. The ceiling ratio λ will be varied from \$30,000 to \$150,000 per QALY for the CEAC analysis. The cost-effectiveness hypothesis will be tested against the \$100,000 per QALY maximum willingness to pay norm.

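### The only ICER formulas are labelled for dementia patients, but Secondary Aim 2 and its $100,000 per QALY hypothesis concern all screened versus non-screened subjects

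*Combined protocol and SAP*

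**What the plan says.** The Secondary Aims at the front of the document frame the economic question for everyone screened: "We hypothesize that screened subjects will have an Incremental Cost Effectiveness Ratio (ICER) below the maximum acceptable threshold of" $100,000 per QALY at 12 months. Section I repeats this scope: "Secondary Aim 2 estimates the cost effectiveness of the dementia screening program in comparison to the" no-screening condition. On costs, the same section says "Total medical care utilization costs will be estimated for the control and screening groups".

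The ICER sentence opens at the same level. It "will compare the no screening and less resource intensive usual care treatment strategy (UC) with the screening coupled with the more intensive treatment intervention". It then ends by "using the following formulas for (1) dementia patients (AP) and (2) Dementia patients plus their caregivers (CG"). Two formulas follow, labelled AP and AP+CG. Both have the same right-hand side: (COST_HABC − COST_UC) ÷ (QALY_HABC − QALY_UC). No other ICER is defined, and later in that section the $100,000 hypothesis is tested.

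Three other places bear on who the dementia patients are:

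- Section F requires "no previous diagnosis of dementia or memory problem as determined by ICD-9 codes" or by anti-dementia prescriptions.
- In the screening arm (section E, Screening Process), the MIS-T is given after randomisation, and those who screen positive are referred for diagnostic assessment.
- Controls (The Usual Care Control Groups) receive usual care, "including a referral to the local memory care practices if their primary care provider suspects the presence of a cognitive problem". Section H, Dementia Recognition, adds a search for ICD-9 codes during follow-up.

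**The concern.** A cost-effectiveness ratio for a screening programme should set the cost of screening everyone against the health effect on everyone. That includes people who screen negative, decline work-up, or are worked up and found not to have dementia. A ratio for dementia patients answers a different question.

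Here it also loses the protection of randomisation. Known dementia is excluded at entry, so membership of the set is settled afterwards by a process that the intervention changes. Even a single ICD-9 rule applied to both arms would depend on arm, because screening generates diagnoses that usual care would not. Cases found by screening and cases noticed by a provider need not be alike in severity, utility or cost.

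An analyst who follows the formulas and one who follows the aim would report different quantities against the same threshold. Only the second would test the stated hypothesis.

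**Working it through.** **1. The plan's own figures.** For 0.094 SD, two-sided α = 0.05 and 80% power, a two-mean calculation gives 1,777 per arm, or 3,554 in total. Dividing by 0.90 gives 3,949, against 3,951 stated. At 1,800 per arm the four table effects give 77.9%, 85.1%, 86.4% and 91.0%, as printed. The effect sizes are therefore used below as stated. The plan gives no sample size or power for the ICER.

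**2. Subjects left out (Screening Process).** Screened: 2,000. Positive: 15% × 2,000 = 300. Of these, about 100 refuse work-up, 100 are found not to have dementia and 100 are diagnosed. If the dementia set means those diagnosed, the subjects left out are 1,700 + 100 + 100 = 1,900 of 2,000 (95%). This counts people outside the formulas. Some refusers and screen-negatives may have dementia.

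**3. Share of the assumed benefit in the non-demented (Statistical Power).** The text scenario assumes 0.40 SD in demented and 0.06 SD in non-demented subjects.

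*At the stated 85% sensitivity and 15% prevalence:* detected cases are 0.15 × 0.85 = 0.1275 of the arm and contribute 0.1275 × 0.40 = 0.0510.

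- If missed cases gain nothing, the non-demented contribute 0.85 × 0.06 = 0.0510. The share is 0.0510/0.1020 = 50%.
- If missed cases are grouped with the non-demented, they contribute 0.8725 × 0.06 = 0.0524. The share is 0.0524/0.1034 = 51%.

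These totals are 0.102 to 0.103, not the stated 0.094, so the stated effect does not follow from these two inputs alone.

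*At the weight implied by each stated observable effect:* w = (observable − non-demented) ÷ (demented − non-demented), and share = (1 − w) × non-demented ÷ observable.

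| Demented | Non-demented | Observable | w | Share |
|---|---|---|---|---|
| 0.40 | 0.06 | 0.094 | 0.100 | 57% |
| 0.4 | 0.07 | 0.102 | 0.097 | 62% |
| 0.4 | 0.08 | 0.110 | 0.094 | 66% |
| 0.3 | 0.07 | 0.091 | 0.091 | 70% |
| 0.3 | 0.08 | 0.100 | 0.091 | 73% |

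The weights are back-solved; the plan does not state them. At 15% prevalence, a weight near 10% leaves some demented subjects in the remainder, so the shares are approximate.

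**4. Control-arm cases.** The plan gives no number. As an assumption, take 6% prevalence (section L) to 15% (Statistical Power): 0.06 × 2,000 = 120 to 0.15 × 2,000 = 300 cases. Take 0% to 25% as recognised in usual care. That gives 0 to 0.25 × 300 = 75 controls, against about 100 diagnosed in the screening arm. The 25% is borrowed from the team's earlier cohort (section D), where it is an upper limit on recorded diagnosis in moderate-severe impairment.

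**5. Discounting.** Section I applies 3% a year over two years, but section E gives 12 months of follow-up. At year end one year's factor is 1/1.03 = 0.971. It applies to costs and effects alike, so it largely cancels in the ratio.

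**The case against.** The best counter-argument is that a whole-arm ratio was intended. The COST and QALY terms are indexed by strategy, the sentence opens with a comparison of strategies, and medical costs are to be estimated for both groups. The AP and AP+CG labels could then mark whose costs and QALYs count. This is possible, and it means that the loss of randomisation follows only from the literal reading. It does not remove the conflict: the text still says dementia patients, and costs by arm do not define a QALY difference by arm.

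A reader might infer that screening costs are left out. The documents do not support that. Section I divides costs by phase, with screening as one phase, costs the activity needed to run the programme, and varies the "overhead cost rate for the screening and coordinated care management". What is missing is only a statement that these costs for the whole screening arm enter COST_HABC.

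A reader might also take the shares in step 3 as the part of the QALY gain that is lost, or as the error in the ICER. They are 12-month HUI differences in SD units and say nothing about cost. Nor do the documents show that the literal formulas favour either arm.

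Finally, it is tempting to say that the correction needs no new data at all. HUI is collected on all 4,000 subjects and medical costs by arm, which is enough for the payer perspective. The societal perspective also needs patient and caregiver time. Section I has staff log this in eMR-ABC, the care-coordination software. The plan gives no clear source of time costs for all controls and non-demented subjects.

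**Conclusion.** The concern stands as a conflict within the plan: the aim and hypothesis, the arm-level costing and the ICER labels do not describe the same population, and no all-randomised ICER is defined. Followed literally, the formulas give a non-randomised comparison that does not test the $100,000 hypothesis. They would leave out about 95% of the screening arm at the plan's counts, and about half or more of the assumed HUI benefit. The lower figure rests on the stated sensitivity and prevalence, the higher ones on implied weights. The control-arm range of 0 to 75 is an assumption.

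This should be fixed before the economic data are analysed. It concerns one secondary aim. The HUI, PHQ-9 and GAD-7 comparisons are between randomised groups and are not affected. The identical right-hand sides and the two-year discounting period are minor.

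**What to change.** Make the ICER, net benefit and acceptability curve on all randomised subjects, by assigned arm, the test of the $100,000 hypothesis:

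- **Estimand:** difference in mean cost per subject divided by difference in mean QALYs.
- **QALYs:** from HUI at 0, 1, 6 and 12 months, adjusted for baseline HUI, with deaths valued at 0 (the HUI anchor in section H) and missing HUI handled by the imputation or likelihood methods that section I already lists.
- **Costs:** state that screening and diagnostic work-up costs for the whole screening arm are included.
- **Perspective:** report the payer version from planned data. For the societal version, state that patient and caregiver time is captured only where the plan logs it, and treat time costs for other subjects as an assumption in sensitivity analysis.
- **Dementia-only ratios:** keep as exploratory and non-randomised, with one case definition for both arms.
- **Minor:** give formula (2) its own terms or drop it, and match the discounting period to the 12-month follow-up.

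The cost is SAP wording and some programming. The downside is a smaller QALY difference per subject than in dementia patients alone: the plan's text scenario assumes 0.094 SD across the arms against 0.40 SD in dementia.
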